Study Week	8	11	23	35	47	60	73	86	99	112	125	138	151	164	165	170	
Informed consent							X ^I										
C-SSRS	-	X	X	X	X	X	X	X	X	X	X	X	X	X	X	X	X
Eligibility assessment	X																
Adverse events	-	X	X	X	X	X	X	X	X	X	X	X	X	X	X	X	X
Physical and neurologic (including non-dilated ophthalmic) examinations	-	X	X	X	X	X		X		X		X		X	X	X	X
Dilated ophthalmic examination ^A						X		X ^A		X ^A		X ^A			X ^A		X
Vital signs ^B	-	X	X	X	X	X		X		X		X		X	X	X	X
Weight, body mass index	-	X	X	X	X	X		X		X		X		X		X	X
Electrocardiogram (12-lead)	-	X	X	X	X	X				X				X	X	X	X
AUA Symptom Index	-	X	X	X	X	X		X		X		X		X		X	X
Concomitant medications	-	X	X	X	X	X	X	X	X	X	X	X	X	X	X	X	X
Pregnancy test ^C	-	X	X	X	X	X	X ^I	X		X		X		X		X	X
Clinical laboratory tests	-	X	X	X	X	X		X		X		X		X	X	X	X
QoL assessments (QOLIE-31)	-		X	X	X			X		X		X		X		X	X
Clinical Global Impression of Severity (CGI-S)	X		X	X	X	X	X	X	X	X	X	X	X		X	X	
Patient Global Impression of Severity (PGI-S)	X		X	X	X	X	X	X	X	X	X	X	X		X	X	
Collect eDiary, Issue/Training of paper diary ^D	X																
Collect and compliance check of completed paper diary and issue new paper diary		X	X	X	X	X	X ^I	X		X		X		X	X	return	return
PK blood samples (XEN1101) ^E	-	X				X				X				X			X
Study drug compliance check	-	X	X	X	X	X		X		X		X		X			X

Study Period	Open-label Treatment														Post-Tx Follow-up ^{F,G}		
Visit Number	8A*	9	10	11	12	13A	14A-TC ^I	15A ^I	16-TC	17	18-TC	19	20-TC	21	F1b	F2b	ET
Study Day	56±3	77±3	161±7	245±7	329±7	420±7	511±7	602±7	693±7	784±7	875±7	966±7	1057±7	1148±7	1155±3	1190±10	
Study Week	8	11	23	35	47	60	73	86	99	112	125	138	151	164	165	170	
Dispense study drug to patient	X	X	X	X	X	X	X ^H	X	X ^H	X	X ^H	X	X ^H				

*: Last day of double-blind treatment period. Patients entering the OLE will be dispensed 20 mg QD of XEN1101 and return their previous study drug.

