6 STUDY INTERVENTION

6.1 STUDY INTERVENTION(S) ADMINISTRATION

6.1.1 STUDY INTERVENTION DESCRIPTION

CC1

CC1 The corresponding placebo drug product is formulated as identical-looking capsules filled with
of an inert material. CC1

The study drug and placebo drug product will be packaged in sealed high-density polyethylene (HDPE) bottles, containing 33 capsules/bottle.

The labeling of the IMP will be in compliance with current Good Manufacturing Practice specifications, as described in The Rules Governing Medicinal Products in the European Union, Volume 4, Annex 13, Investigational Medicinal Products, and any other or local applicable regulations.

Sample label(s) will be submitted to the health authorities according to the submission requirements in the appropriate jurisdiction.

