If the IMP is found to be intolerable, and withdrawal from the study is the only alternative for the patient, unless the patient has met dose stopping criteria in [Section 7.2](#) the investigator may temporarily stop the IMP for 1 week within the treatment period: after a one week washout period patients may then be instructed to continue with their assigned IMP, but to reduce the dosing frequency from QD, to once every second day (every other day). The investigator must notify the medical monitor whenever the patient's study drug is temporarily stopped and the dosing interval changed, or permanently stopped for intolerance.

If the every second day dosing regimen is not tolerated, to the level of requiring withdrawal from the study, the patient will be instructed to stop taking the IMP. Patients in whom IMP dosing has been permanently stopped for any reason will be required to complete a site visit one week (7 ± 3 days) following their last dose of IMP (Visit F1a) and to complete a follow-up visit 42 ± 7 days following their last dose (Visit F2a). Patients who withdraw early from the study and are unwilling or unable to complete these follow-up visits, will be requested to complete an early termination visit (Visit ET). Patients will be requested to continue completing their eDiary until the last study visit. Refer to [Table 1a](#) Schedule of Assessments.

OPEN-LABEL EXTENSION PHASE:

Each eligible patient entering the OLE will return the study drug dispensed during the DBP on the Day 56 visit and will receive a bottle of 20 mg capsules of XEN1101. Participants will be instructed to take a single daily 20 mg oral dose of XEN1101 with food at approximately the same time in the evening each day. Participants will be instructed to begin taking their open-label 20 mg dose at least one day after their last dose of double-blind study drug. Participants continuing in the OLE will be supplied with an additional 3 bottles of 20 mg capsules of XEN1101 at the Day 77 Visit and 3 bottles at each subsequent scheduled visit during the OLE treatment period. Subjects who have had their dose reduced to QOD dosing due to intolerance will be dispensed 2 bottles of XEN1101 at each subsequent visit following the dose reduction. (Note: XEN1101 may be sent from the site to patients by courier at the time of telephone call [TC] visits).

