- Blood sample for PK analysis (XEN1101).
- Collect and check completed diary and resupply of new paper diary.
- Compliance check and dispense study drug (20 mg capsules XEN1101).

Visit 10/Study Day 161 (\pm 7 days) – Patients Participating in the OLE

- C-SSRS.
- AEs.
- Physical and neurologic examinations, including ophthalmoscopy.
- Vital signs.
- Weight and BMI.
- 12-lead ECG.
- AUA Symptom Index.
- Concomitant medications, including any changes to AEDs.

- Urine pregnancy test for females of childbearing potential (if positive a serum pregnancy test will be performed).
- Clinical laboratory tests.
- CGI-S.
- PGI-S.
- QoL assessment (QOLIE-31).
- Collect and check completed diary and resupply of new paper diary.
- Compliance check and dispense study drug (20 mg capsules XEN1101).

Visit 11/Study Day 245 (± 7 days) – Patients Participating in the OLE

- C-SSRS.
- AEs.
- Physical and neurologic examinations, including ophthalmoscopy.
- Vital signs.
- Weight and BMI.
- 12-lead ECG.
- AUA Symptom Index.
- Concomitant medications, including any changes to AEDs.
- Urine pregnancy test for females of childbearing potential (if positive a serum pregnancy test will be performed).
- Clinical laboratory tests.
- CGI-S.
- PGI-S.
- QoL assessment (QOLIE-31).
- Collect and check completed diary and resupply of new paper diary.
- Compliance check and dispense study drug (20 mg capsules XEN1101).

Visit 12/Study Day 329 (± 7 days) – Patients Participating in the OLE

- C-SSRS.
- AEs.
- Physical and neurologic examinations, including ophthalmoscopy.
- Vital signs.
- Weight and BMI.
- 12-lead ECG.

- AUA Symptom Index.
- Concomitant medications, including any changes to AEDs.
- Urine pregnancy test for females of childbearing potential (if positive a serum pregnancy test will be performed).
- Clinical laboratory tests.
- CGI-S.
- PGI-S.
- QoL assessment (QOLIE-31).
- Collect and check completed diary and resupply of new paper diary.
- Compliance check and dispense study drug (20 mg capsules XEN1101).

Visit 13A/Study Day 420 (\pm 7 days) – Patients Participating in the OLE

- C-SSRS.
- AEs.
- Physical and neurologic examinations, including ophthalmoscopy.
- Vital signs.
- Weight and BMI.
- 12-lead ECG.
- AUA Symptom Index.
- Concomitant medications, including any changes to AEDs.
- Urine pregnancy test for females of childbearing potential (if positive a serum pregnancy test will be performed).
- Clinical laboratory tests.
- CGI-S.
- PGI-S.

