- QoL assessment (QOLIE-31).
- Blood sample for PK analysis (XEN1101).
- Collect and check completed diary and resupply of new paper diary.
- Compliance check and return of study drug (20 mg capsules XEN1101).
- CCI

Note: Patients who successfully completed 52 weeks of OLE treatment (as per Protocol version 4.1) prior to approval of the amendment in Protocol version 4.2, and in whom it has been <6 months since their last treatment, will be permitted to resume OLE treatment with XEN1101 if they continue to meet study criteria for participating in the OLE. This subgroup of patients will need to reconsent and complete Visit 14A assessments onsite in order to obtain study drug and the paper diary. A urine pregnancy test must be performed for females of childbearing potential (if positive a serum pregnancy test will be performed).

TC Visit 14A/Study Day 511 (± 7 days) – Patients Participating in the OLE

- Reconsent (for patients reentering the OLE)
- C-SSRS.
- AEs.
- Concomitant medications, including any changes to AEDs.
- Urine pregnancy test for females of childbearing potential (if positive a serum pregnancy test will be performed) (for patients reentering the OLE).
- CGI-S.
- PGI-S.
- Provision of study drug (20 mg capsules XEN1101) to patient.

Visit 15A/Study Day 602 (± 7 days) – Patients Participating in the OLE

- C-SSRS.
- AEs.
- Physical and neurologic examinations, including ophthalmoscopy.
- Vital signs.
- Weight and BMI.
- AUA Symptom Index.
- Concomitant medications, including any changes to AEDs.
- Urine pregnancy test for females of childbearing potential (if positive a serum pregnancy test will be performed).
- Clinical laboratory tests.
- CGI-S.
- PGI-S.
- QoL assessment (QOLIE-31).
- Collect and check completed diary and resupply of new paper diary.
- Compliance check and return of study drug (20 mg capsules XEN1101).

- CCI

TC Visit 16/Study Day 693 (\pm 7 days) – Patients Participating in the OLE

- C-SSRS.
- AEs.
- Concomitant medications, including any changes to AEDs.
- CGI-S.
- PGI-S.
- Provision of study drug (20 mg capsules XEN1101) to patient.

Visit 17/Study Day 784 (\pm 7 days) – Patients Participating in the OLE

- C-SSRS.
- AEs.
- Physical and neurologic examinations, including ophthalmoscopy.
- Vital signs.
- Weight and BMI.
- 12-lead ECG.
- AUA Symptom Index.
- Concomitant medications, including any changes to AEDs.

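### Section 8.1 lists return of study drug but no dispensing at OLE Visits 13A, 15A, 17 and 19, in conflict with Table 1b and Section 6.1.2

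*Combined protocol and SAP*

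**What the plan says.** Three parts of the protocol govern supply in the OLE.

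- **Section 8.1, visit lists.** At Visits 9 to 12 the drug line is "Compliance check and dispense study drug (20 mg capsules XEN1101". At Visits 13A, 15A, 17 and 19 it is "Compliance check and return of study drug (20 mg capsules XEN1101", and no other visible line mentions supply. Visit 21, the last treatment visit, carries the same return line. The telephone visits between them (14A, 16, 18 and 20) each list provision of drug.
- **Section 1.2, Table 1b.** The row "Dispense study drug to patient" is marked at every visit from 8A to 20 and not at Visit 21.
- **Section 6.1.2, open-label phase.** After the Day 77 visit, patients on daily dosing receive "3 bottles at each subsequent scheduled visit during the OLE treatment period". Patients reduced to every-second-day dosing receive 2 bottles. Section 6.1.1 describes bottles "containing 33 capsules/bottle".

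Two further statements matter. The OLE part of Section 8.1 says that subsequent visits follow Table 1b as well as the lists below it. Section 4.1 puts the last scheduled dose on Day 1148.

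**The concern.** Dosing is meant to continue through Visits 13A, 15A, 17 and 19, yet at these four visits Section 8.1 uses the line it uses at the end of treatment. The change from dispense (Visits 9 to 12) to return (from Visit 13A on) reads as deliberate to anyone using the list as a working checklist.

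If a site acted on the list alone, the patient would hand back remaining capsules and receive none until the next telephone visit. The stakes are an unplanned interruption of treatment in patients with epilepsy, and damage to the data on long-term safety and maintenance of efficacy for which Section 4.3 says the OLE exists. Exposure and capsule-count compliance in OLE Years 2 and 3 would also become hard to interpret if sites resolved the conflict differently.

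**Working it through.** **Visit spacing.** Section 4.1 places telephone visits 3 months between site visits in Years 2 and 3. Table 1b gives Weeks 60, 73, 86 and so on to 164, which is 13 weeks = 13 × 7 = 91 days. The study days agree: "Visit 13A/Study Day 420", then "TC Visit 14A/Study Day 511", then "Visit 15A/Study Day 602", and so on at the same step.

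**Alignment of the Table 1b row.** The row has 13 marks, matching the 13 visits from 8A to 20. Footnote H, on provision of drug from the site, falls on 14A, 16, 18 and 20, which are exactly the telephone visits. The four site visits in question are therefore marked.

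**Is a supply line normally listed in Section 8.1?** Tables 1a and 1b together mark 2 + 13 = 15 dispensing visits. Section 8.1 has an explicit supply line at 11 of them: Visits 3, 6, 8A, 9, 10, 11, 12, 14A, 16, 18 and 20. The missing ones are 15 − 11 = 4: Visits 13A, 15A, 17 and 19.

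**Worst-case gap: all leftover drug handed back, list followed alone.**

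| From | To next provision | Days |
|---|---|---|
| 13A (420) | 14A (511) | 91 |
| 15A (602) | 16 (693) | 91 |
| 17 (784) | 18 (875) | 91 |
| 19 (966) | 20 (1057) | 91 |

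Each visit has a window of ±7 days, so one gap runs from 91 − 14 = 77 to 91 + 14 = 105 days.

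**Gap if leftovers are kept (daily dosing, full adherence, nominal dates).** Capsules received by Visit 13A are 33 at Visit 8A plus 4 × 99 at Visits 9 to 12, that is 429. Capsules used are 420 − 56 = 364. The balance is 65, so the gap after 13A is 91 − 65 = 26 days. Each telephone visit then supplies 3 × 33 = 99 capsules for 91 days, which leaves 8. The gap after each of 15A, 17 and 19 is 91 − 8 = 83 days. One telephone-visit supply cannot bridge two intervals (2 × 91 = 182 capsules needed against 99).

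**Supply if Table 1b and Section 6.1.2 are followed.** 99 capsules against 91 days leaves 8 spare, and there is no gap at nominal dates.

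**The redacted bullet.** In Section 8.1 a redacted closing bullet appears at Visits 1, 2, F1a, early termination (double-blind), 13A, 15A, 17, 19, F1b and early termination (OLE). These are the ten columns marked for the dilated ophthalmic examination in Tables 1a and 1b. Six of the ten have no dispensing mark (1, 2, F1a, F1b and both early-termination visits). At Visits 9 to 12 dispensing sits in the compliance line itself and not in a separate bullet. The hidden text is therefore unlikely to be a dispensing line, but the match does not reveal what it says.

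**The case against.** The strongest reply is that Section 8.1 does not stand alone. It tells sites to conduct OLE visits according to Table 1b as well as the lists, so a site that follows it in full also follows the dispensing row. Section 6.1.2 and the continuation of dosing to Day 1148 point the same way. This stands, and it means that the gap is a risk and not an instructed outcome.

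Second, return need not exclude resupply. Patients bring their bottles to site visits for a capsule count (Section 6.4), and on Day 28 of the double-blind period they hand back one bottle and receive another. On that reading the four lists are merely incomplete. This stands in part. At Visit 6, however, where both steps occur, Section 8.1 lists both; and at Visit 21 the identical line does mean return without resupply.

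Third, the wording may be a leftover. Visit 13A is (420 − 56) / 7 = 52 weeks into the OLE, and some patients completed a 52-week OLE under protocol version 4.1. An old end-of-treatment line may have been carried over and copied forward. This is plausible but is inference, and it would explain the conflict without removing it.

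A reader might infer that patients will be off drug for 4 × 91 = 364 of the 1148 − 420 = 728 days from Visit 13A to Visit 21, or 50%. The documents do not support that. It would require a site to set aside Table 1b and Section 6.1.2, collect every leftover capsule, and do so at all four visits.

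**Conclusion.** The point holds as an internal inconsistency in operative supply instructions: at four OLE visits the visible Section 8.1 drug line disagrees with Table 1b and Section 6.1.2. It is not a flaw of design, and the text does not clearly withhold drug.

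The possible consequence is a supply gap up to the next telephone visit. The 91 days (77 to 105 with windows) are a worst case, resting on two assumptions: the site relies on the list alone, and all remaining drug is handed back. If leftovers are kept, the figures are about 26 days after Visit 13A and 83 days after each of the other three, for daily dosing with full adherence. The conclusion also rests on the inference that the redacted bullet is not a dispensing line.

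Only OLE exposure, compliance and long-term data are at issue. The double-blind primary analysis, its type I error and its power are untouched. The correction is worth making because it removes a risk of treatment interruption at almost no cost.

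**What to change.** Reconcile the drug lines for Visits 13A, 15A, 17 and 19 in Section 8.1, the dispensing row of Table 1b and the open-label supply rule in Section 6.1.2, so that all three give one supply instruction. Where both return and dispensing are meant at a visit, list both, as Section 8.1 does at Visit 6. Which instruction is intended is for the sponsor to state. Notify sites of the reconciled text.

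The cost is four lines in an amendment or a site memo, with no change to the analysis.

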8.2 EFFICACY ASSESSMENTS

8.2.1 SEIZURE TYPES

Seizure information will be collected on an ongoing basis by patient use of the eDiary throughout the baseline, DBP, and follow-up for patients not participating in the OLE, which will be reviewed at selected visits as specified in [Table 1a](#) (Schedule of Assessments). For patients participating in the OLE, the eDiary will be replaced with a paper diary at Visit 8 (end of DBP).

The following seizure types according to the ILAE 2017 classification ([Fisher et al., 2017](#)) will be recorded:

- Focal aware seizures.
- Focal impaired awareness seizures.
- Focal motor onset seizures (including subtypes).
- Focal non-motor onset seizures (including subtypes).
- Focal to bilateral tonic-clonic seizures.
- Generalized onset motor seizures (including subtypes).
- Generalized onset non-motor seizures (including subtypes).
- Unknown onset motor seizures (tonic-clonic and epileptic spasms).
- Unknown onset non-motor seizures.

8.2.2 SEIZURE/IMP/RESCUE MEDICATION DIARY

Patients will be instructed to complete a daily seizure diary for the entire duration of the study including the planned 8-week baseline period through post-treatment follow-up. An eDiary will be used to record type and frequency of seizures, IMP compliance, and administration of rescue medications. For patients participating in the OLE, the eDiary will be replaced with a paper diary at Visit 8 (end of DBP).

Training on the use of the eDiary will be provided at the Investigators Meeting and/or at the site initiation visit. Site staff will be responsible for training the patient on the use of the eDiary and back-up paper diary at the baseline visit and as required throughout the study. Details regarding provision of devices, training and data collection are located in the Study Operations Manual. Training on the use of the OLE paper diary will be provided during routine monitoring visits or through web casts.

8.2.3 QUALITY OF LIFE SURVEYS

Patients will complete the Quality of Life in Epilepsy (QOLIE-31; [Cramer et al., 1998](#)) questionnaire at the selected visits as specified in [Table 1a](#) and [Table 1b](#) Schedule of Assessments.

8.2.4 GLOBAL IMPRESSION SCALES

The CGI scale ([Forkmann et al., 2011](#); National Institute of Mental Health [NIMH]) will be administered by a trained physician at selected visits as specified in [Table 1a](#) Schedule of Assessments. The CGI-S scale will be administered at selected visits during the OLE, as specified in [Table 1b](#) Schedule of Assessments.

The PGI-C scale (NIMH) will be provided to the patient for completion at selected visits as specified in [Table 1a](#) Schedule of Assessments. The PGI-S will be provided to the patient for completion at selected visits during the OLE, as specified in [Table 1b](#) Schedule of Assessments.

8.3 SAFETY, PHARMACOKINETIC, AND OTHER ASSESSMENTS

8.3.1 PHYSICAL, NEUROLOGIC, AND OPHTHALMOSCOPY EXAMINATIONS

Full physical and neurologic examinations (including ophthalmoscopy examination) will be performed at selected visits as specified in [Table 1a](#) and [Table 1b](#) (Schedule of Assessments).

The neurological examination will include evaluation of the patient's mental state including a cognitive assessment; cranial nerves II-XII including visual acuity, visual fields, and fundoscopy; motor and reflexes; gait and coordination; and sensation.

8.3.2 VITAL SIGNS

Vital signs (blood pressure and pulse) will be measured in semi-supine position after the patient has rested comfortably for at least 5 minutes; 3 measurements should be taken within 15 minutes and the average result entered in the eCRF. After the resting measurements, an orthostatic blood pressure test should be performed: blood pressure and heart rate measured within 2 to 5 minutes after standing up. Vital signs (including the orthostatic test) will be measured at each study visit prior to taking any blood samples as specified in [Table 1a](#) and [Table 1b](#) Schedule of Assessments.

Weight will be measured in kilograms or pounds at selected visits as specified in [Table 1a](#) and [Table 1b](#) Schedule of Assessments. Measurements should be taken with patients wearing light clothing and without shoes using a calibrated scale for all measurements.

Height will be measured in centimeters or inches at the initial screening visit.

8.3.3 ELECTROCARDIOGRAPHIC MEASUREMENTS

A 12-lead ECG will be performed at selected visits as specified in [Table 1a](#) and [Table 1b](#) Schedule of Assessments. ECG printouts will be filed in the patient's source documents for medical safety reviews.

Each ECG recorder will be set-up to the required technical specifications and containing the information required to identify the records. Each ECG recording will be clearly identified (patient identification [ID], visit date, and the actual times of ECG recordings).

Twelve-lead ECG recordings will be taken after the patients have been resting in a semi-supine position for at least 10 minutes. The patients will avoid postural changes during the ECG recordings and site staff will ensure that patients are awake during the ECG recording.

All recorded ECGs will be reviewed by the investigator or medically qualified designee, and the review will be documented in the source. If a patient shows an abnormal ECG, a repeat ECG will be conducted. A cardiologist review of abnormal ECG tracings will be requested if deemed necessary by the investigator.

8.3.4 AMERICAN UROLOGICAL ASSOCIATION SYMPTOM INDEX

Patients will be administered the AUA Symptom Index ([Barry et al., 1992](#)) at selected visits as specified in [Table 1a](#) and [Table 1b](#) Schedule of Assessments.

8.3.5 CLINICAL LABORATORY TESTS

Blood and urine specimens will be collected last, after recording vital signs (including orthostatic test) according to the schedule shown in [Table 1a](#) and [Table 1b](#) Schedule of Assessments. Patients with lab samples that were not obtained or cannot be analyzed, may be requested to return for an unscheduled

visit. Laboratory determinations will be performed by Medpace Reference Laboratories, located in Cincinnati, Ohio, United States (US) and Leuven, Belgium.

Laboratory evaluations will include the following:

Hematology	Biochemistry	Urinalysis
Platelet count	Aspartate aminotransferase (AST)	Leukocytes
Hemoglobin	Alanine aminotransferase (ALT)	Nitrite
Hematocrit	Alkaline phosphatase	Urobilinogen
White blood cells (WBC)	Blood urea nitrogen (BUN)	Protein
Neutrophils	Gamma-glutamyl transferase (GGT)	pH
Eosinophils	Bicarbonate	Blood
Basophils	Creatinine	Specific gravity
Lymphocytes	Cholesterol	Ketones
Monocytes	Uric acid	Bilirubin
Red blood cells (RBC)	Total serum proteins	Glucose
Reticulocyte count	Albumin	Appearance
	Glucose	Color
	Sodium	Urine microscopy (if applicable)
	Potassium	
	Calcium	
	Phosphorus	
	Chloride	
	Creatine kinase	
	Lactate dehydrogenase (LDH)	
	Bilirubin (total and direct)	

